### Abstract

Epidemiological estimates suggest that approximately 11,390,400 Americans, and 90,300 Veterans in VA care experience symptoms for months after initial COVID-19 infection, a phenomenon known as Sequelae of Sars CoV-2 infection (PASC) or more colloquially known as Long-COVID. Common symptoms of Long-COVID include prolonged fatigue, impairment of memory, concentration disorder, headache, pain, insomnia, anxiety, post-traumatic stress disorder (PTSD), and depression. Longer term effects of COVID-19 have been reported in all age groups and demographics including persons with asymptomatic, mild, or severe initial COVID-19 infection. A recent VA-based Nature publication representing the largest cohort of Long-COVID patients studied to date (n= 73,435 non-hospitalized patients with COVID-19, 13,654 hospitalized patients with COVID-19 and 5 million other VA patients without COVID-19) reported on 6-month outcomes post-infection. Long-COVID patients had an increased risk of death, use of health resources, and a substantial burden of health loss spanning multiple organ systems. Post COVID-19 VA patients also showed increased mental health problems including sleep disorders, anxiety disorders, trauma and stress-related disorders as well as used more opioid and non-opioid pain medications, antidepressants, and sedatives to treat these conditions. These findings are critical to estimating the impact of Long-COVID on Veterans, who may have unique vulnerabilities due to increased incidence of trauma, physical, and psychiatric risk factors.

Long-COVID Coping and Recovery (LC-CR) is a promising new manualized psychotherapeutic intervention focusing on illness management, functional improvement and moving towards recovery from Long-COVID. This study will pilot test the acceptability and feasibility of LC-CR. The treatment aim is to improve psychological adjustment to Long-COVID symptoms, promote resilience, and facilitate coping, based on skills training, acceptance-based and identity-based principles. The results of the proposed study will provide data to 1) identify adaptations needed to optimize LC-CR for Veterans with Long-COVID; 2) identify possible benefits of LC-CR; 3) inform development of a large scale RCT of LC-CR for Veterans with Long-COVID.

### List of Abbreviations

Provide a list of all abbreviations used in the protocol and their associated meanings.

AE	Adverse Event
CHIME	Connectedness; Hope and optimism about the future; Identity; Meaning in life; and Empowerment.
CPRS	Computerized Patient Record System
LC-CR	Long-COVID Coping and Recovery
MERS-CoV	Middle East Respiratory Syndrome Coronavirus
OCC	Office of Connected Care
PASC	Post-Acute Sequelae of Sars CoV-2 infection
SAMHSA	Substance Abuse and Mental Health Services Administration
SARS-CoV	Severe Acute Respiratory Syndrome Coronavirus
VA CONNECT	VA Caring for Our Nation's Needs Electronically during the COVID-19 Transition
VHA	Veterans Health Administration
VVC	VA Video Connect

## 2.0 Introduction

Epidemiological estimates suggest that approximately 11,390,400 Americans, and 90,300 Veterans in VA care experience symptoms for months after initial COVID-19 infection, a phenomenon known as Post-Acute Sequelae of Sars CoV-2 infection (PASC) or more colloquially known as Long-COVID. Common symptoms of Long-COVID include prolonged fatigue, impairment of memory, concentration disorder, headache, pain, insomnia, anxiety, post-traumatic stress disorder (PTSD), and depression (Taquet et al., 2021). Longer term effects of COVID-19 have been reported in all age groups and demographics including persons with asymptomatic, mild, or severe initial COVID-19 infection. Despite Long-COVID symptoms resulting in significant functional impairment, there are few empirically supported treatment approaches specifically designed to address this population. Many in the field contend that given the complexity and variability of Long-COVID manifestations, successful treatment cannot be considered from a single organ point of view, but rather require a patient-tailored multidisciplinary approach that steps beyond amelioration of psychological symptoms (Ambrosino et al., 2021; Lerner et al., 2021). Long-COVID treatment requires specialists across medical, neurological, rehabilitation, and mental health fields in conjunction with recovery-based approaches such as Whole Health, and Chaplain Services.

Our proposed intervention, Long-COVID Coping and Recovery (LC-CR), aims to improve psychological adjustment to Long-COVID symptoms, promote resiliency, and facilitate coping, all of which can impact functional status and quality of life. LC-CR is designed to help to build a relevant and personally meaningful action plan to address the symptoms Veterans may be experiencing due to Long-COVID and to assist Veterans with Long-COVID in managing their illness, increasing function, and moving towards recovery. LC-CR focuses on psychological adjustment and coping, and augments medical, rehabilitation, and neurological treatment for this population. Our approach is based on the CHIME model of personal recovery which includes five overarching processes: 1) Connectedness; 2) Hope and optimism about the future; 3) Identity; 4) Meaning in life; and 5) Empowerment. We will target the CHIME processes using established psychotherapeutic techniques such as skills training, acceptance-based and identity-based principles. Our integrative approach will incorporate rehabilitative strategies from specialists treating Long-COVID patients (e.g., pulmonologists; nutritionists; chaplains; rehabilitation therapists, etc.) with the focus of restoring functional capacities, fostering resiliency, and bolstering life satisfaction.

Our ability to access the Icahn School of Medicine at Mount Sinai's COVID Registry longitudinal data, and leadership in our local James J. Peters VA's Long-COVID Clinical Recovery Center, coupled with our expertise in recovery-based psychotherapy (see preliminary studies), we are uniquely poised to pilot an innovative treatment for Veterans with Long-COVID.

Based on adaptations from existing recovery-based and COVID-19 distress group interventions that our team has developed/piloted, we have developed a treatment framework that consists of twenty 75-minute weekly sessions. The therapy will be divided into two modules consisting of 8 sessions each (16 sessions total): Module 1 (the first 8 sessions) will target more immediate symptoms and Long-COVID related issues as part of the recovery process. Module 2 (the second 8 sessions) will focus on more long-term recovery and creating a meaningful and purposeful future. We specifically are designing a group intervention to build support and mitigate the loneliness associated with chronic conditions such as Long-COVID. The core sessions will focus on the impact of Long-COVID on mental and physical health, teach coping skills to foster resiliency and hope, identify barriers to employment/education due to Long-COVID, and review relapse prevention.

## 3.0 Objectives

**Overall Goal:** To pilot a Long-COVID psychotherapeutic intervention, “Long-COVID and Recovery” (LC-CR) while collecting pilot data to assess its acceptability and feasibility.

**Aim 1:** Identify adaptations needed to optimize LC-CR for Veterans with Long-COVID through veteran and stakeholder consultation.

**Aim 2:** Identify possible benefits of LC-CR.

**Aim 3:** Inform development of a large scale RCT of LC-CR for Veterans with Long-COVID.

### 3A) Significance

#### Long-COVID in the VA:

A recent VA-based *Nature* publication representing the largest cohort of Long-COVID patients studied to date (n= 73,435 non-hospitalized patients with COVID-19, 13,654 hospitalized patients with COVID-19 and 5 million other VA patients without COVID-19) reported on 6-month outcomes post-infection (Al-Aly et al., 2021). Long-COVID patients had an increased risk of death, use of health resources, and a substantial burden of health loss spanning multiple organ systems. Post COVID-19 VA patients also showed increased mental health problems including sleep disorders, anxiety disorders, trauma and stress-related disorders as well as used more opioid and non-opioid pain medications, antidepressants, and sedatives to treat these conditions (Al-Aly et al., 2021). The authors also found that the severity of initial COVID-19 infection predicted later Long-COVID symptom severity. A recently published report on one-year longitudinal follow-up data on hospitalized COVID-19 patients, noted statistically significant increases in anxiety or depression from the six-month to twelve-month time points (Huang et al., 2021). **These findings are critical to estimating the impact of Long-COVID on Veterans, who may have unique vulnerabilities due to increased incidence of trauma, physical, and psychiatric risk factors** (Marini et al., 2020; Na et al., 2021; Hill et al., 2021).

#### Previous coronavirus epidemics demonstrated long term psychiatric sequelae:

The two global epidemics from coronavirus outbreaks include Severe Acute Respiratory Syndrome Coronavirus (SARS-CoV) and Middle East Respiratory Syndrome Coronavirus (MERS-CoV); both left survivors with fatigue, persistent shortness of breath, reduced quality of life and significant mental health problems (O’Sullivan, 2021). A Lancet meta-analysis of MERS and SARS psychiatric sequelae noted post-infection point prevalence of post-traumatic stress disorder (32.2%), depression (14.9%), and anxiety disorders (14.8%) and a mean return to work of almost three years (Rogers et al., 2020). Also concerning was the lengthy duration of psychiatric symptoms; up to 4 years for SARS-CoV (Lam, 2009) Moreover, one third of SARS survivors experienced a psychiatric disorder 30 months post infection (Mak et al., 2009). **These statistics highlight the prevalence and chronicity of mental health sequelae of CoV infections.**

#### Long-COVID and Functional Impairment:

There is a growing literature recognizing the negative impact of Long-COVID on functioning in individuals with severe presentations of COVID-19 requiring hospitalization (Olezene et al., 2021; Daunter et al., 2021), and also more mild cases (Jacobson et al., 2019; Havervall et al., 2021). Colleagues at Stanford University examined longitudinal functional outcomes in 118 COVID+ patients, including 22 who were hospitalized (18%; Jacobson et al., 2019). Four months post infection, in those with employment, 11.5% missed work and just under 40% reported health-related impairments at work. For the full cohort, approximately 50% reported health-related impairment in daily activities. Long-term impairment at home or at work did not differ by initial hospitalization status highlighting the chronicity of dysfunction extending to less severe presentations. Similarly, a report of healthcare providers with COVID-19 noted that a considerable portion of low-risk individuals with mild COVID-19 infection reported a diversity of long-term symptoms, and that these symptoms disrupted work, social, and home life (Havervall et al., 2021). While research examining the direct impact of COVID-19 on functional impairment is limited at this point, past work among other medical illnesses suggests that that the link between disease severity and functional impairment is moderated by co-occurring mental health symptomatology (i.e. anxiety and depression; Kim et al., 2000). Similarly, anxiety sensitivity has been found to moderate the impact

of COVID-19 perceived stress on functional Impairment (Julious, 2005) **This data highlights the importance of addressing mental health symptoms directly to positively impact functional status.**

#### **Mental health treatment for Long-COVID patients:**

Despite Long-COVID symptoms resulting in significant functional impairment, as of yet, there are few empirically supported treatment approaches specifically designed to address this population. Many in the field contend that given the complexity and variability of Long-COVID manifestations, successful treatment cannot be considered from a single organ point of view, but rather require a patient-tailored multidisciplinary approach (Ambrosino et al., 2021; Lerner et al., 2021).

#### **Recovery-oriented care is a valuable approach to helping Veterans:**

The traditional medical model of mental illness focuses on treating mental illness as a disease and on finding a 'cure' leading to the absence of clinical symptoms. However, in recent years, mental health recovery has been understood to extend beyond remission of symptoms. During the 1980s, through a deepening understanding of the lived experience of those suffering from mental illness, recovery was understood to involve living a fulfilling, rewarding life, even with the ongoing presence of mental illness (Taquet et al., 2021). Recovery was seen to involve positive changes in how people think about and experience themselves which may occur regardless of whether they experience symptom reduction or improved function (Taquet et al., 2021). There have been several attempts to provide concrete frameworks for 'recovery'. The Substance Abuse and Mental Health Services Administration (SAMHSA) has developed a working definition of 'recovery' from mental illness; "a process of change through which individuals improve their health and wellness, live a self-directed life, and strive to reach their full potential" (p. 3; Leamy et al., 2011). SAMHSA, in 2012, identified ten guiding principles to recovery (Hope, Person-Driven, Many Pathways, Holistic, Peer/Ally Supported, Relationships/Social Network Supported, Culturally Based, Addresses Trauma, Involves Strengths/Responsibilities, and Respect; Leamy et al., 2011). Finally, an influential review of 89 studies focusing on personal recovery in mental health found five overarching recovery processes with high levels of relevance to clinical research and practice: 1) Connectedness; 2) Hope and optimism about the future; 3) Identity; 4) Meaning in life; and 5) Empowerment (summarized with the acronym '**CHIME**'; [name] et al., 2020). A study with 7 focus groups (N=57) found individuals receiving recovery-oriented mental health care report increases in CHIME areas ([name] et al., 2021). **The CHIME recovery framework fits with the overall VA mental health mission and has increasingly been implemented in the VAMC system as well as nationally and internationally** (Marini et al., 2020).

### **3B) Innovation**

#### **Applying recovery model to Long-COVID:**

The VHA is a leader in the movement towards recovery-oriented mental health care, which focuses on creating collaboration between users and providers guided by the user's vision of the life they want to lead. There is a need to apply recovery approaches from chronic illnesses as this approach best matches the trajectory of Long-COVID patient's needs. Within this paradigm, interventions will focus on positive identity, growth through Long-COVID related challenges, building optimism, connection, personal control and meaning in order to improve functioning and quality of life. In addition, our treatment includes integration of a skills development approach for facilitating increased coping and building resilience.

#### **Long-Term Impact:**

Given the number of individuals who have been or will be infected with COVID-19, the public health impact will continue to be profound. The VHA will undoubtedly be greatly affected by the lasting impact of infection. As of August 19, 2021, the VHA has diagnosed over 300,000 Veterans with COVID-19 infection, 273,732 convalescent cases and 13,254 deaths (data from the VA COVID-19 National Summary website). If only a small fraction of SARS-CoV-2 infections lead to longer term effects, the burden of disease will be significant. Despite large numbers of individuals experiencing post-COVID symptoms and psychiatric sequelae (upwards of 30%); (Logue

et al., 2021), impacting quality of life and functional status, few empirically validated treatment approaches exist, and none in the Veteran population.

## 5.0 Study Procedures

## 5.1 Study Design

**Group Intervention.** Veterans will participate in a LC-CR group (75 minutes 1x/week for a total of 16 sessions) via the HIPAA-compliant telehealth platform VA Video Connect (VVC) in accordance with the Office of Connected Care (OCC)'s best telehealth practices. VA WebEx will be available as an approved back-up telehealth platform in the event of VVC technical difficulties.

The intervention will be delivered in two modules consisting of 8 sessions each (16 sessions total):

**Module 1:** The first 8 sessions of the treatment will focus on skill based coping strategies to target more immediate symptoms and Long-COVID related issues as part of the recovery process.

**Module 2:** The second 8 sessions will focus on more long-term recovery and creating a meaningful and purposeful future.

Sessions will be co-facilitated by [name] and another co-therapist. [name] will be the co-therapist for Module 1 of therapy (first 8 sessions) and [name] will be the co-therapist for Module 2 of therapy (second 8 sessions).

**Timeline:** (See **GANTT chart**) For the first 3 months we will complete the needs assessment interviews. In months 4-7, we will revise the psychotherapy workbook and therapist manual *and will consult with stakeholders monthly for input on revisions throughout our piloting phases*. In months 18-24, we will develop and submit a RR&D Merit grant application for an RCT to test the treatment.

Project dates: 10/1/22- 9/30/24	Year 1				Year 2			
	Q1	Q2	Q3	Q4	Q1	Q2	Q3	Q4
Activity	October - December (2022)	January-March (2023)	April-June (2023)	July-September (2023)	October-December (2023)	January-March (2024)	April-June (2024)	July-September (2024)
IRB								
Train RA and other startup activities								
Complete PACS needs assessment								
Analyze needs assessment results								
Finish developing psychotherapy materials and therapist manual								
Consult with stakeholders on proposed intervention and revise materials								
Run first set of pilot group								
Revise treatment based on trial participants and stakeholder feedback								
Run second set of pilot groups								
Present findings								
manuscript preparation								
Merit preparation/sSubmission								

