**Developing an Integrative, Recovery Based, Post-Acute COVID-19 Syndrome (PACS)
Psychotherapeutic Intervention, “PACS Coping and Recovery”**

Funding Agency: Rehabilitation Research and Development Service (RR&D) Small Projects in Rehabilitation Research (SPiRE).

NCT05453201

June 1, 2024

JJPVAMC

PI: [name]

Co-I: [name]

Co-I: [name]

Co-I: [name]

All statistical analyses were conducted using the RStudio (version 4.4.2). Item-level missingness (< 0.5% item-level observations) was handled with participant-mean imputation. Little's (1988) missing completely at random (MCAR) test was not significant ($p > .05$) indicating that the data were missing at random. Paired-sample t-tests were used to examine changes in primary and secondary outcomes from pre- to post-treatment. Paired Wilcoxon tests were used when the Shapiro-Wilk test was significant ($p < .05$). The significance level was set at $p < .05$ for all analyses.

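### The SAP's paired tests treat each Veteran's change as independent although LC-CR is given in therapy groups; if change is positively correlated within groups and the result is meant to reach beyond the groups run, the p-values are too small

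*Protocol*

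**What the plan says.** The SAP is one short section. Its outcome analysis is: "Paired-sample t-tests were used to examine changes in primary and secondary outcomes from pre- to post-treatment". The alternative is: "Paired Wilcoxon tests were used when the Shapiro-Wilk test was significant". The threshold is .05 throughout. The SAP has no therapy-group term, no group-level analysis and no caveat about group delivery.

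The protocol describes group delivery. Section 5.1: "Veterans will participate in a LC-CR group (75 minutes 1x/week for a total of 16 sessions". Section 2.0 makes contact between members part of the rationale: "We specifically are designing a group intervention to build support and mitigate the loneliness". There is more than one group, since the 5.1 timeline table has a row "Run second set of pilot groups". Section 5.2 gives a ceiling of 36 Veterans. Neither document states how many groups there are or how large they are.

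Protocol 5.6 plans repeated-measures mixed models across the time points. It names no therapy-group term, and the SAP does not carry these models forward.

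**The concern.** Both SAP tests take the change scores as independent observations. Veterans who share 16 weekly sessions, in a format chosen for mutual support, may improve or fail to improve together. With positive correlation within groups, 36 change scores carry less information about a wider population of groups than 36 independent ones. The paired test does not see this, and switching to Wilcoxon does not help, because that test makes the same assumption.

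What is at stake is the reporting of Aim 2 (Protocol 3.0): "Identify possible benefits of LC-CR". An outcome flagged at p < .05 could look better supported than it is.

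**Working it through.** **Inputs.** From the documents: group delivery (Protocol 5.1), at most 36 Veterans (5.2), paired t or paired Wilcoxon at .05 (SAP; two-sided assumed, as sidedness is not stated). Assumed, because the documents do not give them: equal groups in layouts of 6x6, 4x9 or 3x12 for N = 36 and, allowing for attrition, 6x4, 4x6 or 3x8 for N = 24 (groups x members); ICC of change 0.01 to 0.10. The documents contain no sample-size or ICC calculation to reproduce.

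**Step 1: standard error.** Let change = group effect + individual error, with total variance 1. For k groups of m, DEFF = 1 + (m-1) x ICC and the variance of the mean is DEFF/N. The paired test uses s²/N, where s² has expectation 1 - (DEFF-1)/(N-1). So

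true SE / reported SE = sqrt(DEFF / (1 - (DEFF-1)/(N-1))).

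- N = 36, smallest (6x6, ICC 0.01): DEFF = 1.05; sqrt(1.05/0.9986) = 1.025.
- N = 36, largest (3x12, ICC 0.10): DEFF = 2.10; sqrt(2.10/0.9686) = 1.47.
- N = 24: from 1.016 (6x4, ICC 0.01) to 1.32 (3x8, ICC 0.10).

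At N = 36 a reported p of .05 then corresponds to 2 x (1 - Phi(1.96/ratio)), about .056 to .18.

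**Step 2: type I error.** Null simulation, 40,000 replicates, groups drawn at random, paired t-test at nominal 5%:

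| Layout | ICC 0.01 | ICC 0.05 | ICC 0.10 |
|---|---|---|---|
| 6x6 (N = 36) | 5.6% | 8.0% | 10.8% |
| 4x9 (N = 36) | 6.0% | 9.5% | 14.4% |
| 3x12 (N = 36) | 6.4% | 11.5% | 17.7% |
| 6x4 (N = 24) | 5.2% | 6.5% | 8.8% |
| 4x6 (N = 24) | 5.4% | 8.0% | 11.0% |
| 3x8 (N = 24) | 5.8% | 8.9% | 13.1% |

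A separate run with 100,000 replicates gave 5.4-17.6% for the N = 36 layouts. The Wilcoxon test lies within about one point of the t-test. At ICC 0 and N = 36 the paired t-test rejects in 4.9-5.0%.

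**Step 3: the inference target.** When the group effects are instead held fixed and average zero, so that the question is mean change in the groups actually run, the paired t-test rejects in about 4-5%. There is then no inflation.

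**Step 4: a group-level check.** A t-test on the k group-mean changes, with k-1 df, holds 4.7-5.2% in all the layouts above. Its 95% half-width is t(k-1) x sqrt(DEFF/N). At ICC 0.05:

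- N = 36: 2.571 x sqrt(1.25/36) = 0.48 SD (6 groups); 3.182 x sqrt(1.40/36) = 0.63 SD (4); 4.303 x sqrt(1.55/36) = 0.89 SD (3). Paired test: 2.030/6 = 0.34 SD.
- N = 24: 0.56, 0.73 and 1.02 SD for 6, 4 and 3 groups, against 0.42 SD.
- Two groups of 18: DEFF = 1.85; 12.706 x sqrt(1.85/36) = 2.9 SD, which is of no practical use.

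**The case against.** The strongest reply has four parts.

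- **Inference target.** The inflation needs the therapy groups to stand for a wider population of groups. For a pilot asking about possible benefits, a summary of the groups actually run is defensible, and for that the paired test is not too liberal (step 3). This stands, and the point is conditional on it.
- **Unknown size.** ICC and layout are assumptions. Protocol 5.1 describes one facilitator throughout with one co-therapist per module, so the text gives no basis for adding differences between therapists. Negative correlation within groups would make the p-values too large. All of this stands. It leaves shared group experience as a plausible source, but not a measured one.
- **Little depends on it.** The adequacy criteria and targets in 5.5 concern attendance, recruitment and clinician hours, and 5.6 leaves efficacy to a later RCT. With no control arm, a small p-value could not attribute change to LC-CR in any case. This stands and limits the importance.
- **Weak remedy.** A group-mean analysis has few degrees of freedom, and with unequal groups it weights groups rather than Veterans. This also stands. It is a reason to use that analysis only as a sensitivity interval beside the paired result.

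A reader might also infer that the pooled pre/post result mixes two versions of the treatment, because the timeline table lists "Revise treatment based on trial participants and stakeholder feedback" between the rows for the two sets of groups. The documents do not establish that. It rests on row order in a chart whose timing cannot be read from the text, and 5.1 has revision input running throughout piloting, so set is not a clean version boundary.

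**Conclusion.** The point holds as a low-priority reporting matter. The SAP's outcome tests ignore therapy group. Their p-values are too small under two conditions together: change is positively correlated within groups, and the result is meant to apply beyond the groups run. Under the assumed layouts and ICCs, the effect runs from negligible (about half a point of type I error) to material (about 18% against 5%). The documents do not show where this pilot falls.

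A reader might infer that the reported p-values are in fact wrong, or that a go/no-go decision is compromised. Neither follows: no ICC or group layout is given, and no decision rule uses these p-values. Nor can one assume that the protocol's mixed models would have dealt with the issue, since 5.6 mentions only comparison across time points.

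**What to change.** - Keep the paired analysis. Report mean change with a 95% CI, and the number and size of therapy groups.
- With at least three groups, add one sensitivity interval from the group-mean changes (k-1 df). Say that it weights groups equally and that a wide or non-significant result does not show absence of benefit. With two groups, show the group means only.
- State that the paired tests assume independence between members of a group, and label all outcome p-values as descriptive.
- Label the addition post hoc. The SAP is in the past tense and already reports a result: Little's "missing completely at random (MCAR) test was not significant".
- Estimates by first and second set are optional description, not a test of treatment version.

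A random group effect is not proposed. With 3 to 6 groups and 36 Veterans, its variance is estimated at or below zero in 30-58% of simulated runs at ICC 0.01-0.10, which returns essentially the paired-test SE.

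The cost is a few lines of reporting and one extra interval from existing data. The downside is that interval's width: at N = 36 and ICC 0.05, 0.48-0.89 SD against 0.34 SD.
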